LOCF	Last Observation Carried Forward
MHRA	Medicines And Healthcare Products Regulatory Agency
MRI	Magnetic Resonance Imaging
NIMP	Non-Investigational Medicinal Product
QA	Quality Assurance
REC	Research Ethics Committee
SAE	Serious Adverse Event
SD	Standard Deviation
SPC	Summary Of Product Characteristics
SUSAR	Suspected Unexpected Serious Adverse Reaction
TCC	Total Contact Cast

Protocol version 1**Evaluating plantar foot pressure in a novel diabetic offloading device****IRAS code 198005****PROTOCOL SYNOPSIS**

GENERAL INFORMATION	
Short Title	Evaluating plantar foot pressure in a novel diabetic offloading device
Full Title	Does a novel diabetic offloading boot (PulseFlow DF) reduce the plantar foot pressures compared to usual standard care? A proof of concept pilot study
Sponsor	University of Leeds
Sponsor ID	
MREC No.	
Chief Investigator	[name]
Principal Investigator	[name]
Co-ordinating Centre	University of Leeds, School of Healthcare
National / International	Local
STUDY INFORMATION	
Phase	Proof-of-concept
Indication	Evaluation of a new CE marked device (PulseFlow DF) for the treatment of diabetic foot ulcers
Design	Proof of concept
Number of sites	One
Study Objective	To compare plantar foot pressures between prescribed usual standard of care and the PulseFlow DF boot.
Secondary Objective(s)	Explore the effectiveness and acceptability of the novel device.
Study Endpoint	Collection of data from a single appointment.
Secondary Endpoint(s)	NA
STUDY TIMELINES	
Expected start date	February 2017
Subject enrolment phase	February 2017 to July 1 st 2017.
Follow-up duration	No follow up
End of Study Definition	Numbers needed to recruit reached (n36)
Expected completion date	June 2017
STUDY SUBJECT INFORMATION	
Number of study subjects	36

Protocol version 1**Evaluating plantar foot pressure in a novel diabetic offloading device****IRAS code 198005**

Age group of study subjects	18 plus
Inclusion criteria	
Diabetes
 
Plantar forefoot diabetic foot ulcer over the 1st, 2nd, 3rd, 4th or 5th metatarsal joints
 
Neuropathic or Neuro-Ischaemic classification foot ulcer
 
Orthotic intervention for offloading/usual standard
 
Plantar forefoot ulceration over the metatarsal heads

Exclusion criteria	
Charcot Arthropathy
 
ABPI of <0.8 and >1.29
 
Temporary footwear
 
Accommodating or footwear not designed to offload.
 
Clinically active Infection causing swelling
 
Purely ischaemic classification foot ulcer
 
Current active osteomyelitis
 
Patients with forefoot trans metatarsal amputations
 
Fractures of the foot
 
Due to alterations in gait, patients with diagnosed vascular dementia, Parkinson's, alcoholism or other major medically related gait alterations i.e. intoxication, brain cancers, muscular degeneration diseases, inflammatory arthritis, etc. This does not include osteoarthritis.
 
Major amputees
 
Pregnancy
 
Participating in another trial regarding foot dressings or off loading

Protocol version 1**Evaluating plantar foot pressure in a novel diabetic offloading device****IRAS code 198005****SCHEMATIC DIAGRAM**

[figure not shown]
2017	Jan	Feb	Mar	Apr	May	June	July	Aug-Dec
Submit ethical & R&D approval Audit Categories proportions Scoping able participants Non study Patient specific gait analysis testing								
Receive ethical & R&D approval Consent Identification of patients through database Approach patients in routine appointment Provide written literature								
Recruit Patients Contact and Consent Second follow up phone or appointment contact Written consent at laboratory appointment Data collection in gait lab								
Statistical Analysis Data analysis Statistical analysis Member checking usability outcomes								
Close Study Results writing Research conclusion with written research project Poster presentation PPI and research group meeting								

Protocol version 1

Evaluating plantar foot pressure in a novel diabetic offloading device

IRAS code 198005

Patient Contact Schematic

1. INTRODUCTION

1.1. Background

Prevalence

Diabetes is an endocrine disorder which carries considerable health risks. Worldwide estimates from the International Federation of Diabetes (IDF 2016) estimate the prevalence of diabetes to be 387 million people. In the next twenty years this is set to rise to an estimated 582 million people which is 10% of all adults. Estimates (Gonzalez et al., 2009) show that from 1996 to 2005, the diabetic population rose by 50% in the United Kingdom (UK). Diabetes UK estimates currently 4 million people are living with diabetes (Diabetes UK, 2015)

Aetiology

Treating diabetes includes its co-morbidities and has proved challenging due to the rising population. Diabetes can cause damage to the nerves and circulation to the lower extremities which can result in the complication of Diabetic foot ulcers (DFU). It is estimated that 25% of the diabetic population will develop a DFU in their lifetime (Ndip and Jude, 2009). The prevalence of diabetic foot ulcers in a European based population of Type 1 and Type 2 Diabetes is 5.5% (Abbott et al., 2005). DFU's are linked to poorer quality of life, higher lower limb amputations and higher mortality rates following amputation (Singh et al., 2005). This is important as neuropathy is the highest cause of DFUs (Parisi et al., 2016), and a strong predictor of lower extremity amputations (Krishnakumar et al., 2015).

Other causes of developing a DFU can be helped by separating DFUs into different causes alongside neuropathy, which are:-

- Neuropathic (caused by lack of sensation)
- Ischaemic (caused by lack of blood supply)
- Neuro-ischaemic (caused by a mix of both sensation and blood supply deficits)

Common classifications have proven difficult to accept amongst clinicians. A widely used system has been incorporated into clinical practice which incorporates the above classification called the "Texas Classification" (Armstrong et al., 1998).

DFUs are consistently considered a chronic wound with increased risk of amputation, infection, suffering and death (Jeffcoate and Harding, 2003). Diabetic foot ulcerations are mainly caused by the damage to the peripheral nerves that causes a loss of protective sensation. This allows the insensate skin to be damaged from direct pressure or trauma without the patient realising (Konstantikaki, 2008). This pressure can increase over certain areas of the foot leading to tissue damage or a break in the skin resulting in the DFU. This is then perpetuated due to a lack of feeling (no pain) resulting in an inability to relieve

Protocol version 1

Evaluating plantar foot pressure in a novel diabetic offloading device

IRAS code 198005

pressure over the ulcer site to allow appropriate healing. The DFU is a chronic wound caused by (Jeffcoate and Harding, 2003):-

- Nerves that help small blood vessels controlling microcirculation to the skin are damaged delaying new skin formation
- Motor function controlled by nerves are damaged changing the foot mechanics causing hard skin to build increasing pressure areas
- Poor medical management including diagnosis, access to the right specialists and patients being unaware of the condition

These and other factors related to diabetes such as depression, impairment of the inflammation process for healing due to hyperglycaemia and delayed access to a specialist treatment centre causes healing to be complex (Jeffcoate and Harding, 2003, Konstantikaki, 2008). The associated outcomes such as hospitalisation, infections, minor or major amputations can have a lasting impact. The estimated cost in socio-economic terms varies widely. One of the largest and most recent European study showed on average the total direct and indirect costs for treating an ulcer to healing and major amputation is €7,772 to €25,222 respectively (Prompers et al., 2008). This is based on 2005 monetary treatment prices. The monetary cost burden to patients is also a factor but is rarely reported (Cavanagh and Bus, 2010). Other effects on patients include physical and emotional issues having negative impacts to their quality of life. This has been shown to be significantly reduced in diabetic patients with foot ulcerations (Jaksa and Mahoney, 2010).

The healing of DFU is therefore paramount to avoiding such devastating disease outcomes such as amputations, cost and other patient related factors. One of the priority interventions to promote healing of DFUs is allowing the foot to be rested or offloaded whilst the patient can continue a reasonable level of independence. The offloading of the foot relies on specific techniques guided by evidence based guidelines (NICE, 2015).

Previous Studies

Elevated diabetic plantar foot pressure has been identified as clinically significant in the development and deterioration of DFUs (Lavery et al., 2003). This is through tissue damage from numerous mechanical pressures on the foot (Yavuz et al., 2015). The clinical practice of pressure relief to treat DFUs is synonymous with offloading and relates to the pressure relief at sites of diabetic foot ulceration. This has been based on clinical experience and has lacked good quality research evidence. However, a recent systemic review (Bus et al., 2016a) has helped guide

Protocol version 1

Evaluating plantar foot pressure in a novel diabetic offloading device

IRAS code 198005

clinicians on effectiveness of interventions chosen rather than rely on the historical experiences of clinicians. This review provides strong evidence towards the use of total contact casting, prefabricated irremovable and removable devices as the primary choices to offload DFUs. This is based on empirical research in studies using non complicated purely neuropathic ulcers in economically developed countries. Additionally reported with consistency in these studies is the evidence that poor adherence results in poorer clinical outcomes therefore further research is needed to measuring and improving adherence to offloading devices. This is important as there is such low use of total contact casting clinically. Ulcer healing relates to the time offloading devices are used and the quality of pressure relief provided by the devices used (Armstrong et al., 2003). The NICE Guidelines CG19 relating to off-loading is based on the Cochrane review on “Pressure-relieving interventions for treating diabetic foot ulcers” (Lewis and Lipp, 2013). This review identifies five out of seven studies showing an associated statistically significant improvement of the number of foot ulcers healed with non removable casts rather than removable. This was expressed as a risk ratio total at 1.41 as likely to heal ulcers (30days, 12weeks and 16weeks) in a non removable device versus a removable device.

The management of providing off loading is complex with many patients opting for removable devices due to lifestyle, job requirements, caring needs, driving and regular ulcer evaluations and/or re-dressings. Other removable pressure relieving devices included temporary therapeutic shoes and removable pressure relieving devices e.g. rigid rocker bottom sandals with non custom insoles, forefoot wedge/off-loading shoes, custom made therapeutic footwear and insoles, Aircasts and other removable casted walkers. It is likely that patients would prefer an option to use an aesthetically acceptable pressure relieving device such as the PulseFlow DF. However there is currently no such evidence for its efficacy in off loading.

Types of pressure affecting the skin

Since there are different types of pressures or forces that can cause damage to the skin there are different ways of measuring this in terms of the outcomes being researched. This study is observing plantar pressure over time which is described in section 1.2. However, offloading or pressure relief can be confused with terms such as force, friction and shear.

Friction and Shear Pressures

Recently there has been an association of shear and friction with DFU (Yavuz et al., 2015, Giacomozi et al., 2008). Force is used as simply a measure of influence that changes movement or an interaction between structures. In the case of the foot this is measured in units of newtons (n) observing force vectors or lines of

Protocol version 1

Evaluating plantar foot pressure in a novel diabetic offloading device

[figure not shown]
IRAS code 198005

pressure on the foot, Figure 1. Friction and shear are two other different forces compared to plantar pressures described in this study, which are associated with DFUs but often used in error describing pressure on the foot.

Friction

Friction is a mechanical force describing when two parallel surfaces pass one another i.e. skin of the foot, and its supporting structure (shoe or floor for example), Figure 1. Friction on a structure (foot on the floor) is associated by the pressure exerted from the downward force. The friction occurs when two surfaces in contact with each other move against each other. Although this is associated with DFUs, research has highlighted the importance that reducing friction force is associated more with preventing rather than healing of DFUs (Braun et al., 2014).

Figure 1.

Shear

[figure not shown]
Shear is a mechanical force exerted directly parallel to the body's surface (skin) which initiates a parallel shift causing shear within the tissues below or above it, Figure 2. Shear has only recently experienced interest from specialists in the treatment of DFUs (Yavuz et al., 2015, Giacomozi et al., 2008). Clinically this can be evidenced regularly when dressings over macerated tissues covering a DFU cause separation of the macerated tissue from the dermal epidermal junction of skin (Braun et al., 2014). Shear is highlighted due to the diabetes effect on skin tissue mechanics and the role of skin biochemical changes related to ulcer formation and the inability to dissipate shear (Zhu et al., 2011).

Protocol version 1

Evaluating plantar foot pressure in a novel diabetic offloading device

IRAS code 198005

Figure 2.

Shear and friction relating to DFU is difficult to measure. Custom built tools have had to be used previously to allow appropriate research (Yavuz et al., 2007). There is no common validated reliable device to perform shear or friction evaluations to show effectiveness on healing DFU compared to plantar pressure relief. Therefore it is unrealistic to be able to measure the shear and friction elements associated with DFU within this study and this study will measure downward or a vertical force.

1.2. *Rationale for the proposed study*

Diabetic Foot Ulcer impacts (including cost)

The impacts from diabetes are both patient related and healthcare based. DFU is associated with a high mortality rate at 34% at 1 year. There is an associated higher limb amputation rate from DFU than other causes. The high mortality rate, high amputation rate and increased socio-economic burden means providing high quality evidence based DFU service provision should be a NHS priority. Offloading is recognised as the priority treatment for healing neuropathic and neuro-ischaemic plantar foot ulcers (NICE, 2015). Since the provision of non removable devices or total contact casts (TCC) is poor, options have to be available that are equivalent in effectiveness at off loading and healing DFU. By improving the quality of offloading choices and acceptability for devices this will improve healing rates and reduce the cost burden where currently in the UK diabetic foot care in 2015 accounted for 0.6%/585.5million pounds of the NHS budget (Diabetes UK, 2015, NHS England, 2016). The evidence for effectiveness of non removable devices is poor. Therefore any device that offloads to the equivalent or more than previous devices and current usual standard of care must be evidenced. The new PulseFlow DF boot is such a device which claims to off load but has little or no

Protocol version 1

Evaluating plantar foot pressure in a novel diabetic offloading device

IRAS code 198005

evidence on DFU subjects. Thus the primary aim of this study is to observe forefoot plantar pressures in a cross sectional purposively selected sample compared to usual standard of care.

How pressure relief is studied

Pressure is measured in a standard unit of kilopascals (kPa). This can be measured by either a static plate embedded in the floor that a person walks across or an in-shoe device. There are several devices to measure pressure including the Pedar-xf analyser (novel, no date). The important considerations for use of such instruments are reliability and repeatability. The Pedar-xf has shown good levels of repeatability and reliability from linear loading with low errors measuring the coefficient of reliability at less than 10% for 93.4% of the parameters tested (Putti et al., 2007). This is practically due to the fact no two steps are identical to produce a 100% repeatable result. There is also good repeatability of loading at high pressures, seen in diabetic foot ulcer patients, as previous studies use healthy individuals (Hurkmans et al., 2006). The in-shoe device uses pressure cells imbedded in an insole which is placed between the foot and the device being measured. The insoles are 1-2mm in thickness. The sensors imbedded in them can detect pressure in kPa. The Pedar-xf analyser being used in this study for example has 99 sensors imbedded in a single insole. Since the interest is measuring pressure between a foot and a new offloading diabetic boot the appropriate instrument would be an in-shoe device.

The Pedar-xf Analyser System

The Pedar-xf system allows dynamic plantar foot pressures to be collected in-shoe simultaneously in both feet. Once this has been achieved the software can be instructed to apply masks to parts of the foot (Putti et al., 2007). The masking helps measure specified regions of the foot (Lavery et al., 2003, Hughes et al., 1993) such as the first metatarsal phalangeal joint. This allows clinicians to identify specific areas targeting specific off loading treatments such as recurrent ulceration sites and explore potential changes to plantar pressures (Arts et al., 2012, Ledoux et al., 2013).

Generating Outcome Measurements

Since pressure can be measured, the outcomes can generate data on contact area (cm^2), area under the peak pressure time curve (pressure time integral or pti) and peak plantar pressure (ppp) known as the single highest pressure calculated in kPa. The parameter of pressure time integral is less significant than ppp in risk factors for ulceration i.e. preventing DFUs (Bus and Waaijman, 2013). However in reducing pressure over an ulcer site rather than reducing the risk of ulceration, the

Protocol version 1

Evaluating plantar foot pressure in a novel diabetic offloading device

IRAS code 198005

pressure time integral could be considered to be of greater significance (Yavuz et al., 2007). Healing requires reducing the pressure over the DFU preventing further tissue damage and promoting healing by redistributing pressure measured by both ppp and pressure time integral. Specialist have debated the issue of both these measurements value and there is no consensus to which one or both to use especially with ppp showing low sensitivity and low specificity to ulcer risk factors (Yavuz et al., 2007, Yavuz et al., 2015, Bus et al., 2016b, Lavery et al., 2003). One of the conclusions was a hypothesis that there must be more complicated diabetic pathology to developing diabetic foot ulceration than just elevated ppp or pressure time integral. The degree of pressure deemed damaging to the DFU is from the length of time in contact (contact time) and the amount of pressure in kPa measured at the interested site(s). It has been highlighted (Ledoux et al., 2013) that there is no consensus on the range of kPa that causes damage (DFU) as studies show numerous variables that affect the measures such as size of pressure cells, static platform or in-shoe measuring devices, site of DFU and sampling techniques within research. Therefore concentrating on the devices used in DFU clinical practice to reduce pressure over DFU sites is more important to heal the skin damage than finding the DFU preventative range of kPa on a patient's foot. The priority is therefore identifying whether this new pressure relieving device changes (redistributes pressure effectively) plantar pressure distribution effectively at the common site (forefoot) of diabetic foot ulcerations.

Sampling Rationale

The Texas classification (Armstrong et al., 1998) of DFUs helps identify patients suitable for pressure relief, being neuropathic or neuro-ischaemic. As this is the classification system used at the study site it will be used within the context of this study. The proportion of wound classifications within the local population is as follows, purely ischaemic 10%, purely neuropathic 54%, neuro-ischaemic 36%. Ischaemic DFU prevalence in the UK ranges from 10% to 60% (Ndip and Jude, 2009). Therefore the maximum sample within this centre, 90% (Neuropathic plus Neuro-ischaemic), should be primarily treated by TCC or removable off loading devices (NICE, 2015). Within a 2015 audit within this centre only a small proportion (3%) of the neuropathic and neuro-ischaemic population are receiving the recommended standard of off loading with TCC. This is due to issues around patient consent, clinical capacity and funding making the PulseFlow DF boot and other removable devices as suitable alternatives.

While it is proven the non removable TCC is an effective modality for the successful treatment of diabetic forefoot plantar ulcers related to neuropathy, there are factors making it unsuitable for patients. This pragmatic approach to the sample population is supported by research (Wu et al., 2008) and also by the local

Protocol version 1

Evaluating plantar foot pressure in a novel diabetic offloading device

IRAS code 198005

scoping audit showing poor utilisation of TCCs. Current comparative alternatives to TCCs (similar to the PulseFlow boot) show a low percentage of patient use (7% of the total possible). This highlights the reality of current clinical practice which is similar to the provision of pressure relief in the United States (US). According to specialist (Wu et al., 2008) DFU teams in the US show a lack of and even non existence of following standards on pressure relief for treating neuropathic related DFU's. The products used for pressure relief are bespoke devices, prefabricated devices or bespoke TCC's. There is a lack of products to choose from with limitations for devices used including financial constraints, stigma issues, quality of pressure relief, staff knowledge and skills needed to prescribe them. The direct material cost is lower for the TCC but demands more clinical time, highly experienced and trained staff with patient attending weekly applications. Patient consent to a TCC appears to be low aswell impacting on its use which has not been studied but only hypothesised that it is due to the lack of sensation (Piaggesi et al., 2007). Correct classification and providing appropriate pressure relief using the NICE guidelines CG19 needs to be considered carefully and closely monitored to facilitate efficient and effective use.

Hypothesis

Using the novel PulseFlow DF boot is as effective as usual standard care in off loading diabetic plantar forefoot ulcers.

Sample and Population

The population from the Diabetic Limb Salvage Service within Leeds will be used for the sample. This is a specialist centre based on the NICE CG19 guidelines (NICE, 2015) and provides a service to 252 diabetic foot patients (July 2016).

Outcome

To compare the pressure time integral data in kPa between usual standard care and the PulseFlow DF boot.

2. STUDY AIM AND OBJECTIVES

2.1. Study aim

Protocol version 1

Evaluating plantar foot pressure in a novel diabetic offloading device

IRAS code 198005

The aim of the study is to assess the pressure relief in kPa for pressure time integral (PTI) (Melai et al., 2011) over the forefoot between the boot and usual standard of care.

2.2. *Primary objective*

To identify whether pressure time integral is equivalent or not to usual standard of care.

2.3. *Secondary objective(s)*

To measure the acceptability and effectiveness of the new boot.

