3. STUDY ENDPOINTS

3.1. *Primary endpoint*

Due to the study design (proof of concept) the endpoint will be completion of data collection.

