9.2. Hypotheses

Using the novel PulseFlow DF boot is as effective as usual standard care in off loading diabetic plantar forefoot ulcers.

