9.4. Planned analyses

All data will be explored to check for assumptions of normality and homogeneity of variance for each variable, and to assess which statistical tests i.e. parametric or non-parametric test will be more appropriate to explore the data. The assumption of normality will be assessed graphically by histogram, box-plots and confirmed by statistical testing of significance of skewness and kurtosis. The spread, homogeneity and type of data will determine the type of statistical test. The paired t Test is predicted to be the statistical test of choice following statistician advice. This may change due to abnormal distribution of data once collection is complete.

Gait data will be checked for corruption or incomplete results associated with data capture or software error and rectified where possible either at the point of data collection or data analysis.

Exploratory statistical analyses will be performed to identify any potential associations between gait kinematics, clinical data and patient-reported outcomes. We will also explore the data for unexpected findings, including influential outliers, multicollinearity, truncation and missing data.

The primary outcome (section 2.2) will then be compared for systematic differences between the usual standard care and the PulseFlow DF boot using statistical tests based on the assumptions tested previously.

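### The primary question is worded inconsistently (reduces, equivalent or not, as effective as), the planned difference test answers only the title's wording, and no margin or success rule says which answer counts

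*Combined protocol and SAP*

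**What the plan says.** The protocol puts the boot versus usual-care comparison in several ways.

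- Full title (synopsis): "Does a novel diabetic offloading boot (PulseFlow DF) reduce the plantar foot pressures compared to usual standard care". This is directional.
- Section 2.2, primary objective: "To identify whether pressure time integral is equivalent or not to usual standard of care". No direction is given.
- Section 9.2, repeated under the Hypothesis subheading of section 1.2: "Using the novel PulseFlow DF boot is as effective as usual standard care in off loading diabetic plantar forefoot ulcers". This can be read as equivalence or as not worse.
- Section 9.4: the primary outcome, cross-referenced to 2.2, will be "compared for systematic differences between the usual standard care and the PulseFlow DF boot". On the method: "The paired t Test is predicted to be the statistical test of choice following statistician advice". The choice of test may change once the data are in.

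Other statements are neutral. The synopsis objective and the Outcome subheading of 1.2 speak of comparing, 2.1 of assessing pressure relief, and the rationale in 1.2 of observing forefoot pressures.

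Nothing else settles the matter. Section 3.1 reads: "Due to the study design (proof of concept) the endpoint will be completion of data collection". Section 6.2 calls the study exploratory and sets n by a rule of thumb. No margin, significance level or sidedness appears anywhere.

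**The concern.** The title, the objective and the hypothesis call for different decision rules, and the protocol does not say which one applies. Under the literal wording of 2.2, a boot with clearly lower PTI and a boot with clearly higher PTI are both not equivalent, although they mean opposite things for patients. The test in 9.4 fits the title: a significant difference with lower PTI answers it. It does not fit 2.2 or 9.2, because failing to find a difference is not evidence of equivalence.

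What is at stake is how the result is reported. A significant reduction could be presented as the answer to the title. A non-significant result could be presented as confirming the hypothesis. One person collects, analyses and reports the data (9.1), and the test is finalised after data collection (9.4), so nothing in the plan prevents the question from being chosen once the answer is known.

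**Working it through.** **The plan's own figure.** Section 6.2: 12 per group × 3 = 36, which reproduces. It is a rule of thumb, so there is no power, SD or margin behind it to check.

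**What each wording would require.** Let d = PTI in the boot minus PTI in usual care, within patient. Lower is better.

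| Place | Question | Rule it would need | Supplied? |
|---|---|---|---|
| Title | Is d below 0? | Upper 95% limit below 0 | The 9.4 difference test, read with its sign |
| 2.2 | Is d within ±m? | 90% interval inside ±m (two one-sided 5% tests) | No margin, no such test |
| 9.2 | Is d within ±m, or only below +m? | As for 2.2, or upper limit below +m | No margin, no such test |

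**What the planned test can show.** With n = 36 pairs and d in units of the SD of paired differences, the 95% half-width is t(0.975, 35)/√36 = 2.030/6 = 0.338.

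- Suppose the observed d is +0.30 SD (assumed). The interval is 0.30 ± 0.338, or −0.04 to +0.64. This is not significant, yet it is compatible with PTI in the boot being 0.64 SD higher. It cannot support equivalence without a margin above that.
- Suppose the observed d is −0.80 SD (assumed). The 95% interval is −1.14 to −0.46 and the 90% interval is −1.08 to −0.52. The title's question is answered yes. Two-sided equivalence is not shown for any margin below 1.08 SD.

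**How far the wordings can diverge.** These figures come from simulation (400,000 replicates, n = 36, SD of differences 1). Superiority and not-worse are both read from one 95% interval, and equivalence from the 90% interval. The margins and true differences are assumptions, as the documents give neither.

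| True d | Margin m | Superiority | Not worse | Equivalence |
|---|---|---|---|---|
| 0 | 0.5 | 2.5% | 83% | 81% |
| −0.5 | 0.5 | 83% | about 100% | 5% |
| −0.8 | 0.5 | 99.7% | about 100% | 0.0% |

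The 5% in the second row arises because the true difference was set equal to the margin, where an equivalence test passes about 5% of the time by construction. Holding true d at −0.5 SD and varying only the margin gives these chances of declaring equivalence:

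| m (SD) | 0.3 | 0.5 | 0.6 | 0.75 | 0.8 | 1.0 |
|---|---|---|---|---|---|---|
| Equivalence | 0.2% | 5% | 14% | 43% | 55% | 90% |

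Superiority stays at 83% throughout. The divergence therefore runs from nearly total to slight, depending on a margin that the protocol does not state.

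**The case against.** A reader might infer that a better boot succeeds under the title and fails under 2.2, so that the trial's conclusion reverses. The documents do not support that. There is no success rule to fail. Section 2.2 asks whether PTI is equivalent or not, and answering that it is not, because it is lower, is a legitimate answer. The paired comparison in 9.4 and the means and SDs in 9.3 would show a lower PTI as a signed reduction, so a better and a worse boot would not look alike in the results.

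A reader might also take the sentence in 1.2, "any device that offloads to the equivalent or more than previous devices and current usual standard of care must be evidenced", as a third, non-inferiority definition of success. It is a background remark that such devices need evidence, not a criterion for this study.

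The neutral statements of aim, the completion endpoint in 3.1 and the absence of formal sizing all point towards estimation. Nor do the documents give PTI data from which to judge whether a lower PTI is likely. Usual care in 6.7 includes removable boots as well as footwear and insoles, and footwear not designed to offload is excluded (6.3.2).

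All of this stands, and it limits the point to wording and interpretation. It does not remove the mismatch. The stated primary objective still asks something that the planned test cannot answer, and the title and hypothesis still ask different things.

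**Conclusion.** The point holds as an inconsistency in the primary question and a mismatch with its planned test. The title is directional, 2.2 is not, 9.2 is open to two readings, and 9.4 serves only the title. Because no margin, direction or decision rule is fixed, the framing can be chosen after the result is seen.

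Its size cannot be computed from the documents. The simulated figures illustrate it under assumed margins and effects, with n = 36 reached (5.2 allows recruitment to stop earlier). They show that the answer depends on the margin, not that a better boot would be rejected. Two readings are assumed: that the literal sense of the wording in 2.2 is two-sided, and that the title's plantar pressures means PTI, as the Outcome subheading of 1.2 and sections 2.1 and 2.2 indicate. No stated power figure is wrong, since none is given.

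**What to change.** Use one directional question in the title, 2.2, both statements of the hypothesis (1.2 and 9.2) and 9.4, for example: to estimate the paired boot minus usual-care difference in forefoot PTI. Delete the equivalence wording from 2.2. In 9.4, name the signed mean paired difference with its two-sided 95% confidence interval as the primary result. State that lower PTI is favourable, and that a non-significant difference will not be read as equivalence.

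Only if the team wants a not-worse-than claim should it prespecify and justify a margin, in PTI units, before data collection. It would then read the same 95% interval in fixed order: upper limit below the margin first, then upper limit below zero. The fixed order needs no split of the significance level. This option is debatable in an unsized pilot whose documents supply no margin, and justifying one is real work.

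The estimation option costs edits in five places and no patients, visits or measurements. The downside is that the pilot makes no two-sided equivalence claim. Without a margin or sizing for one, its design does not support that claim as it stands.
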